### 9.2 Statistical Analyses

#### 9.2.1 General Approach

Demographic and baseline patient characteristics will be summarized and described as numbers and percentages or means, median, standard deviations, quartiles and range, as appropriate. Pearson's Chi square tests will be applied for categorized data, and Student's t-test and Mann Whitney U tests for continuous variables. Univariate analyses will be used to assess potential factors primary and secondary efficacy

03 Sep 2025

endpoints as laid out below. Data analysis will be performed using the software package STATA. Free text options will be analyzed qualitatively.

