	
confirmed to be cancer relative to the total number of lesions confirmed to be cancer.
 
Sensitivity = (True Positive)/(True Positive + False Negative)
 
Secondary Endpoints
 
 
1. Incidence rates of all adverse events (AEs), adverse device effects (ADEs), and SAEs, from the time of CYTALUX administration through Visit 3
 
2. Sensitivity for cancerous lesions for:             
 
a. FR<math>\alpha</math> positive lesions
 
b. FR<math>\beta</math> positive lesions
 
 
 
 
Exploratory Endpoints
 
 
1. Genomic evaluation of tumor inclusive of, but not limited to:             
 
a. Estrogen receptor/progesterone receptor (ER/PR) status
 
b. HER2 status
 
c. Mismatch repair (MMR) status
 
d. POLE status
 
e. p53 status
 
f. CARIS whole genome sequencing
 
 
 
2. The exploratory endpoint is the detection rate of CYTALUX with NIR imaging for identification of sentinel lymph nodes (SLNs). The detection rate is the proportion of the patients with SLNs detected by CYTALUX and NIR imaging in all enrolled patients.
 

Study Enrollment:	This study plans to enroll 10 subjects.
Study Population:	Adult subjects (>18 years old) undergoing surgery for endometrial cancer
Phase:	Investigator sponsored study (ISS)
Description of Sites/Facilities Enrolling Participants:	Department of Obstetrics and Gynecology Jordan Center for Gynecologic Cancer at Penn Perelman Center for Advanced Medicine [name]

03 Sep 2025

Description of Study Intervention:	CYTALUX™ (PAFOLACIANINE) INJECTION: folate analog ligand conjugated with an indole cyanine green-like dye as a solution in vials containing 1.6 mL at 2 mg/mL. Each subject will be administered a single intravenous dose of not less than 1 hour before and not more than 168 hours (7 days) before initiation of intraoperative NIR fluorescent imaging.  The imaging systems used in this study will be assessed for meeting the criteria for use with CYTALUX™ (PAFOLACIANINE) INJECTION.
Study Duration:	The recruitment period is estimated at 12 months.
Participant Duration:	The maximum duration a subject is in the study is approximately 2 months.

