## 2 INTRODUCTION

### 2.1 Study Rationale

Intraoperative molecular imaging, specifically with pafolacianine (CYTALUX), has proven to be a valuable real-time adjunctive tool in identifying cancerous lesions for adults undergoing surgery for ovarian and lung malignancies. Marketing authorization for pafolacianine was granted by the FDA (trade name CYTALUX) on November 29, 2021.

Based on clinical evidence and experience from the phase 2 and phase 3 open-label trials for ovarian cancer and literature demonstrating the overexpression of FR, it is possible that CYTALUX could improve the surgeon's ability to comprehensively stage and resect all disease in endometrial cancer, which is important for delivering appropriate adjuvant therapy and improving outcomes for patients. Endometrial cancer is increasing in incidence, especially high-risk tumors. Innovative tools are needed to provide treatment for this patient population.

This study aims to explore the indication of CYTALUX™ (PAFOLACIANINE) for endometrial cancer. This study will evaluate the efficacy of CYTALUX™ (PAFOLACIANINE) binding to endometrial cancers to detect macroscopic cancers during cytoreductive surgery and assess the sensitivity as an intraoperative imaging adjunct.

03 Sep 2025

Over 80% of advanced (stage III or IV) or recurrent endometrial carcinomas express folate receptor (FR), a folate binding protein, making this receptor an ideal target for marking most endometrial cancers ([May 2025, Senol 2015](#)). This also makes FR an ideal target for intraoperative imaging of this cancer, facilitating cytoreduction, and potentially improving outcomes in these patients ([Kalli 2008](#)). Chemotherapy does not appear to affect FR alpha (FR $\alpha$ ) expression in endometrial cancer specimens as examined by immunohistochemistry ([Despierre 2013](#)), so prior treatment is unlikely to affect utility of FR $\alpha$  ligands as imaging agents.

Immunohistochemistry for FR of representative samples of resected tissue will be performed. This is essential to interpret the results of CYTALUX™ (PAFOLACIANINE) binding and intraoperative fluorescence imaging. Since cytoreductive surgeries typically have several specimens with large amounts of tumor, representative samples from pathology proven sites of cancer will be tested for folate expression and will be correlated with intraoperative fluorescence imaging.

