Information on genomic markers for patients receiving CYTALUX will be collected and correlated with intraoperative fluorescence imaging to help predict the utility of CYTALUX with NIR imaging.

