### **6.3 Measures to Minimize Bias – Randomization and Blinding**

This trial will be an open-label study with no randomization or blinding. All subjects will receive the study drug.

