#### 8.1.3 Visit 2: Surgery

*[Purpose: To collect data on the performance of intra-operative molecular imaging]*

1. AEs and ADEs will be recorded during and following surgery.

03 Sep 2025

2. After the surgical site is visualized under normal light and/or palpation, the number and location of suspect lesions detected under normal light will be recorded on the schematic using an “O”.
3. Following the assessment by normal light, subjects will undergo fluorescence imaging of the surgical field. Suspect lesions detected under fluorescence imaging will be marked on the schematic using an “X”.
4. All identified suspect lesions will be marked on the schematic (“O”, “X”, or “⊗” as described in [Section 4.1.3](#)) and excised, at the discretion of the Investigator.
5. Sentinel lymph node biopsy will be performed at the Investigator’s discretion per the standard of care.
6. All excised lesions will be sent to the local laboratory for histopathology and immunohistochemistry staining. A unique identifier will be assigned to each excised lesion and the location of each will be recorded along with the unique identifier. If an organ/large section of tissue (e.g. uterus, omentum) with multiple lesions is excised *in toto*, one grossly positive lesion will be utilized for the purposes of calculating sensitivity and FR expression.
7. Histopathology, folate receptor expression, and genomic testing results will be recorded once data is received per institutional practices and timeline.

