## 9 STATISTICAL CONSIDERATIONS

### 9.1 Statistical Hypotheses

- Primary Efficacy Endpoint:
  - The primary efficacy endpoint is the sensitivity of CYTALUX with NIR imaging for detection of malignant lesions. Sensitivity is defined as the proportion of fluorescent light positive lesions that are histologically confirmed to be cancer relative to the total number of lesions confirmed to be cancer.  
Sensitivity = (True Positive)/(True Positive + False Negative)
- Secondary Efficacy Endpoints:
  1. Incidence rates of all adverse events (AEs), adverse device effects(ADEs), and SAEs, from the time of CYTALUX administration through Visit 3
  2. Sensitivity for cancerous lesions for:
    - a. FR $\alpha$  positive lesions
    - b. FR $\beta$  positive lesions
- Exploratory Endpoints:
  1. Genomic evaluation of tumor inclusive of, but not limited to:
    - a. Estrogen receptor/progesterone receptor (ER/PR) status
    - b. HER2 status
    - c. Mismatch repair (MMR) status
    - d. POLE status
    - e. p53 status
    - f. CARIS whole genome sequencing
  2. The exploratory endpoint is the detection rate of CYTALUX with NIR imaging for identification of SLNs. The detection rate is the proportion of the patients with SLNs detected by CYTALUX and NIR imaging in all enrolled patients.

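### Section 9.2.1 names Pearson chi-square for factor analyses in a 10-patient trial, where it is unreliable at patient level and ignores clustering if lesions are the unit

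*Protocol*

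**What the plan says.** Protocol section 9.2.1 fixes the tests for the secondary analyses: "Pearson's Chi square tests will be applied for categorized data", with t and Mann-Whitney tests for continuous variables. It goes on: "Univariate analyses will be used to assess potential factors primary and secondary efficacy" endpoints. It gives no small-sample proviso, no exact alternative and no unit of analysis. It points forward for details, but sections 9.2.2 and 9.2.3 describe no factor analysis.

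The setting is small and has no comparison group. Section 1.1: "This study plans to enroll 10 subjects". Section 6.3: "This trial will be an open-label study with no randomization or blinding".

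The primary endpoint is counted in lesions, "relative to the total number of lesions confirmed to be cancer" (section 9.1). Section 2.1 expects more than one specimen per patient: "Since cytoreductive surgeries typically have several specimens with large amounts of tumor". Section 8.1.3 restricts the count only where an organ or large section is removed whole; then "one grossly positive lesion will be utilized for the purposes of calculating sensitivity and FR expression". The genomic markers are described per patient: "Information on genomic markers for patients receiving CYTALUX will be collected and correlated with intraoperative fluorescence imaging" (section 2.1). The footnote to the Schedule of Activities allows marker results that predate surgery.

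**The concern.** With one arm there are no treatment groups to compare, so the factor analyses are the main place where a two-group chi-square could be used. Pearson's test relies on a large-sample approximation that 10 patients cannot support. The protocol uses an exact method for the primary test but does not carry that choice into the factor analyses.

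A second problem depends on the unit of analysis. A marker takes one value per patient and the outcome is per lesion. A chi-square on lesions would treat several lesions from one patient as independent evidence about that marker.

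At stake is the first exploratory objective, whether genomic markers could predict the utility of the agent. A misleadingly small p-value could influence patient selection in a later study.

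**Working it through.** **Inputs.** From the protocol: 10 subjects; one arm; lesion-level endpoint; Pearson chi-square. Assumed: a nominal level of 0.05 (stated only for the primary test), 1 to 5 lesions per patient, an intracluster correlation (ICC) of 0.1 to 0.5, and sensitivity of 0.5 or 0.8. The protocol gives no error rate for these analyses, so there is no figure to reproduce.

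**Step 1: expected counts.** The smallest expected count is (smaller row total) × (smaller column total) / 10, which is at most 5 × 5 / 10 = 2.5. The usual requirement of 5 cannot be met in any 2x2 table of 10 patients.

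**Step 2: single tables.** The statistic is χ² = n(ad − bc)² / (product of the four margins).
- 5/5 v 2/5: 10 × (5×3 − 0×2)² / (5×5×7×3) = 2250/525 = 4.29, p = 0.038. Fisher: 2 × C(5,2)/C(10,7) = 2 × 10/120 = 0.17.
- 1/2 v 0/8: 10 × (1×8 − 1×0)² / (2×8×1×9) = 640/144 = 4.44, p = 0.035. Fisher: 2/10 = 0.20.
- 1/1 v 0/9: 10 × 9² / (1×9×1×9) = 10, p = 0.0016. Fisher: 1/10 = 0.10.

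**Step 3: true size at patient level.** All tables were enumerated for each split, with a common response rate from 0.01 to 0.99.

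| Split | Pearson, maximum | Pearson at 80% response | Fisher, maximum |
|---|---|---|---|
| 1/9 | 9.0% | 8.7% | 0 |
| 2/8 | 8.7% | 7.4% | 0.7% |
| 3/7 | 6.2% | 2.9% | 1.6% |
| 4/6 | 5.1% | 1.5% | 2.1% |
| 5/5 | 6.2% | 3.8% | 2.1% |

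Averaged over response rates from 0.05 to 0.95, Pearson's size is about 2.5% to 6%, depending on the split.

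**Step 4: lesion outcomes against a patient-level factor.** With k lesions per patient, the variance is inflated by 1 + (k − 1) × ICC. For k = 3 and ICC 0.3 this is 1.6. The effective critical value is then 1.96/√1.6 = 1.55, a true size of about 12%. Beta-binomial simulation under the null (10 patients, factor split 5/5 or 3/7, equal lesion counts, sensitivity 0.5 or 0.8) gives:

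| Lesions per patient | ICC 0.1 | ICC 0.3 | ICC 0.5 |
|---|---|---|---|
| 1 | 3-6% | 3-6% | 3-6% |
| 2 | 4-5% | 5-8% | 8-11% |
| 3 | 7-8% | 12-14% | 17-19% |
| 5 | 10-12% | 19-22% | 27-30% |

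Uneven counts can raise these figures. At sensitivity 0.8, a 5/5 split, ICC 0.5 and a mean of 2 lesions, size is 12.5% with varying counts and about 8% with equal counts. With varying counts averaging 1.5 and ICC 0.1 to 0.7, it is 4-9%.

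**Step 5: alternatives.** Permuting the factor over whole patients kept size at 1.6% to 4.4% in every setting run. Fisher's power for 90% v 30% is 0.37 (5/5), 0.24 (3/7) and 0.05 (2/8). At a 1/9 split it can never reject.

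**The case against.** A reader might infer that the named test would routinely produce false marker associations well above 5%. The patient-level figures do not support that. The largest values are maxima over the response rate, the average is close to or below nominal, and at 80% response three of the five splits fall below 5%. What stands is that the test is erratic and single p-values can mislead.

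A reader might also infer that the protocol prescribes a chi-square of lesions against genomic markers. It does not. Section 9.2.1 does not list the factors, the genomic evaluation is a separate exploratory endpoint, and section 2.1 speaks only of correlation with imaging. The cross-tabulation follows from how the endpoint and markers are defined and is not stated. Folate receptor status is measured on lesions, so Step 4 does not describe that factor.

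The lesion-level inflation rests on lesion counts and an ICC that the protocol does not give. The rule in section 8.1.3 for organs removed whole, and eligibility that does not require advanced disease, make one or two lesions per patient plausible; inflation is then mild. The limit of 2.5 on expected counts applies only to tables of 10 patients. A table of 30 to 50 lesions can exceed 5 in every cell, and there the problem is clustering.

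Finally, an SAP not shown here may settle the unit of analysis, and its absence from the protocol is no fault. That does not remove the point, because the protocol itself names a test that does not suit 10 patients.

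**Conclusion.** The point holds in limited form and should be corrected. From the sample size alone, Pearson chi-square is an unreliable default: true size varies from well below 5% to 9.0%, and it can report significance where the exact p-value is 0.10 to 0.20. Conditional on lesion-level testing of a patient-level factor, inflation is small at one or two lesions per patient with low ICC. It becomes substantial (about 12-30%) at three to five lesions with an assumed ICC of 0.3 to 0.5.

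The consequence is confined to supportive and exploratory analyses. A reader might extend the criticism to the primary result, but section 9.2.2 specifies an exact binomial test there, and this point does not concern it. Nor do these calculations show that the t-test must go; that is optional.

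**What to change.** In section 9.2.1, replace Pearson chi-square with Fisher's exact test for patient-level categorical outcomes. For lesion-level outcomes, specify a permutation test that permutes a patient-level factor across whole patients, or a patient-clustered method. Label all factor analyses exploratory or descriptive.

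The cost is a sentence or two of wording and a few lines of code. The drawback is low power with 10 patients (Step 5), so the counts themselves should carry the report and a non-significant result should not be read as absence of association.

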### **9.2.2 Analysis of the Primary Efficacy Endpoint**

The primary analysis of the primary endpoint will include subjects exposed to CYTALUX™ (pafolacianine) injection and undergo fluorescent imaging (CYTALUX™ (pafolacianine) injection+Imaging) who:

- Received study drug and were evaluated under NIR fluorescent light imaging during surgery

The primary analysis of the efficacy endpoint will be a one-sample test for a proportion via an exact binomial test conducted at the two-tailed alpha level of 0.05. The test will compare the observed proportion against a threshold of 0.10. The efficacy of CYTALUX™ (pafolacianine) injection in combination with fluorescent imaging will be confirmed if the null hypothesis is rejected and the observed proportion is greater than 0.10. The two-sided 95% confidence interval (CI) will also be calculated.

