## **5     STUDY POPULATION**

Adult subjects (>18 years old) who are presumed high-risk patients or have advanced disease, and/or recurrent disease. Pregnant patients will be excluded.

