#### 8.1.2 Visit 1: Infusion

*[Purpose: To infuse CYTALUX™ (PAFOLACIANINE) INJECTION]*

1. Patients with a known allergy to CYTALUX (pafolacianine) will be given pre-medication of 25 mg Benadryl and 4 mg Zofran as prophylaxis approximately 30 minutes prior to the start of infusion, unless a patient has a history of allergy to either drug.
2. A single dose of CYTALUX will be infused IV over 60 minutes
3. AEs will be recorded during infusion of CYTALUX.

Should the patient experience suspected adverse events during infusion, the infusion will be stopped, and the Principal Investigator (PI) will be contacted for discussion and assessment. Per PI discretion, the patient will be treated for symptoms and infusion can be started again to assess for tolerance. If infusion is still not tolerated, amount infused will be recorded and imaging portion of study will proceed.

4. Intraoperative imaging should begin within 1 to 168 hours (7 days) after the completion of infusion.

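### Section 9.2.2 tests pooled lesions as if independent, although each of the 10 subjects can supply several; a confidence interval on that basis can be too narrow

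*Protocol*

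**What the plan says.** Section 9.1 counts the endpoint by lesion: true positives "relative to the total number of lesions confirmed to be cancer". Section 9.2.2 fixes the primary analysis as a "one-sample test for a proportion via an exact binomial test conducted at the two-tailed alpha level of 0.05", compares the result with 0.10, and treats rejection with an observed proportion above 0.10 as confirming efficacy. It adds: "The two-sided 95% confidence interval (CI) will also be calculated". No method is named for that interval.

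The synopsis plans 10 subjects. Three places bear on lesions per subject:

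- Section 8.1.3: "A unique identifier will be assigned to each excised lesion".
- Section 8.1.3 also has a limiting rule. When an organ or large section with multiple lesions is removed whole, "one grossly positive lesion will be utilized for the purposes of calculating sensitivity and FR expression". This works per organ or section, not per subject.
- Section 2.1: "Since cytoreductive surgeries typically have several specimens with large amounts of tumor". Section 5 describes subjects who are "presumed high-risk patients or have advanced disease, and/or recurrent disease".

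Section 9.2.2 defines its analysis set by subject, but neither it nor any other section mentions correlation between lesions of one subject.

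**The concern.** The exact binomial distribution holds when every lesion is a separate, independent trial with the same chance of fluorescing. Lesions from one subject come from one tumour with a common FR background. They also share one infusion and one interval to imaging, which can vary widely between subjects: "Intraoperative imaging should begin within 1 to 168 hours (7 days) after the completion of infusion". Section 2.1 puts FR expression at over 80% of advanced or recurrent tumours, so some subjects may have tumours that hardly take up the agent.

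If detection differs between subjects, 30 lesions from 10 subjects carry less information than 30 independent lesions. The binomial standard error (SE) is then too small, an interval built on it is too narrow, the type I error of the test is not the binomial figure, and one subject with many lesions can dominate the result. In a 10-subject pilot with so low a threshold, the estimate and its interval are the informative output, and these are what clustering damages.

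**Working it through.** **Inputs from the protocol.** 10 subjects (1.1); null 0.10, two-sided alpha 0.05 (9.2.2); FR expression over 80% (2.1). The protocol states no power, expected sensitivity, lesion count or intra-subject correlation (ICC), so there is no design figure to reproduce beyond the nominal alpha.

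**Assumptions.** 2, 3 or 5 confirmed lesions in every subject; a subject is FR-positive with probability 0.8; sensitivity is a in FR-positive and b in FR-negative subjects.

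**Formulas.** Mean sensitivity μ = 0.8a + 0.2b. ICC = 0.8 × 0.2 × (a − b)² / [μ(1 − μ)]. With m lesions each and n = 10m, true SE = √{[μ(1 − μ)/n] × [1 + (m − 1) × ICC]}; the binomial SE omits the last bracket.

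**ICC**

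- 0.90 vs 0.05: μ = 0.73; 0.16 × 0.7225 / 0.1971 = 0.59.
- 0.80 vs 0.10: μ = 0.66; 0.16 × 0.49 / 0.2244 = 0.35.
- 0.90 vs 0.70: μ = 0.86; 0.16 × 0.04 / 0.1204 = 0.05.

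**Standard error, 0.90 vs 0.05.** With 3 lesions each, the binomial SE is √(0.1971/30) = 0.081. The design effect is 1 + 2 × 0.587 = 2.17, so the true SE is 0.119. With 2 each the pair is 0.125 (true) vs 0.099; with 5 each, 0.115 vs 0.063.

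**Coverage of a nominal 95% Clopper-Pearson interval on pooled lesions**

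| Sensitivity, FR+ vs FR− | 2 each | 3 each | 5 each |
|---|---|---|---|
| 0.90 vs 0.05 | 90% | 83% | 73% |
| 0.80 vs 0.10 | 94% | 90% | 82% |
| 0.90 vs 0.70 | 98% | 96% | 94% |

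A Wilson interval in the first row covers 90%, 79% and 70%. If the 30 lesions split 1, 1, 1, 1, 2, 2, 3, 4, 5, 10, Clopper-Pearson coverage is 71% in the first case and 82% in the second. A different model (beta-binomial, true sensitivity 0.5 or 0.7, ICC 0.3 to 0.5, 3 to 5 lesions each) gives the same pattern, 78% to 92%.

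**False declaration at a true sensitivity of 0.10.** The exact test rejects upward from 7/30 (minimum-likelihood p-value) or 8/30 (doubled tail), and from 10/50 under either convention.

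| Source of correlation | 3 each, min. likelihood | 3 each, doubled tail | 5 each |
|---|---|---|---|
| None | 2.6% | 0.8% | 2.5% |
| FR status only (0.125 vs 0; ICC 0.16 × 0.125² / 0.09 = 0.028) | 2.9% | 1.0% | 3.1% |
| Beta-binomial, ICC 0.2 to 0.4 | 5.1% to 7.2% | 2.2% to 3.7% | 7.1% to 10.6% |

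The last row needs a source of correlation beyond FR status.

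**Decision.** With equal counts, the current test passes in over 99.8% of trials under both 0.90/0.05 and 0.80/0.10.

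**The case against.** The strongest reply has four parts.

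1. **The interval is not fixed.** The main harm is to a CI whose method 9.2.2 does not name, and a SAP could name a suitable one. That stands as a condition: the coverage figures apply only to an interval on the binomial basis. The test itself is fixed in the protocol, however, and an interval matched to it is the natural reading.

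2. **The test is hardly harmed.** If FR status is the only source of correlation, false declaration stays near 3%, and at plausible sensitivities the trial passes either way. This also stands, and it is why the point is not graded higher.

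3. **Lesion counts may be low.** Section 5.1 requires only a primary diagnosis and scheduled surgery, with no stage criterion, and the whole-organ rule would leave a subject with disease confined to the uterus with one lesion. If five subjects give 1 lesion and five give 2, Clopper-Pearson coverage is about 95% to 96% in both main cases, so there is no shortfall. Against that, Sections 2.1 and 5 expect more extensive disease, and nothing caps lesions per subject.

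4. **The 0.05 sensitivity in FR-negative subjects is assumed.** True. The milder 0.90/0.70 contrast shows no material loss.

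These points limit the size of the fault. They do not make an independence-based test suitable for clustered lesions.

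**Conclusion.** The concern holds and should be fixed. The endpoint is counted per lesion, the test assumes independent lesions, subjects can supply several, and no section deals with it.

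The consequence depends on two quantities the protocol does not give. With 3 to 5 lesions each and a strong contrast between subjects (ICC 0.35 to 0.59), a nominal 95% binomial interval covers 73% to 90%. With a mild contrast, or with 1 to 2 lesions per subject, the loss is negligible. The type I error exceeds 5% only with substantial correlation at the null, and then not under every p-value convention. The pass/fail decision is little affected at a sensitivity near 0.7. The fault therefore lies mainly in stated precision.

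**What to change.** In 9.2.2, keep lesion-level sensitivity as the estimate and state that the 95% CI and the comparison with 0.10 treat the subject as the cluster. One workable form is the Korn-Graubard interval:

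- Effective n = [p(1 − p)/v] × (t with n − 1 df / t with 9 df)², capped at n, where v is the between-subject variance estimate of p and both t values are 97.5% points.
- Enter this effective n in the Clopper-Pearson formula.
- Efficacy is declared if the lower bound exceeds 0.10.

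**Fallback.** If all or none of the confirmed lesions fluoresce, or the design effect cannot be estimated, use an exact interval with n equal to the number of subjects. For 10 of 10 the lower bound is 0.025^(1/10) = 0.69; treating 30 of 30 lesions as independent would give 0.025^(1/30) = 0.88. The fallback is rarely needed in the two main cases (at most 1.4% of trials). It would apply in 0.95^20 = 36% of trials if sensitivity were 0.95 in everyone with 2 lesions each.

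**Support.** Report subject-level sensitivity: subjects with at least one true-positive lesion among subjects with at least one confirmed cancer. Apply the same clustering rule to any interval for the FRα and FRβ sensitivities.

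**Cost.** Wording only, with no new data or patients. In simulation of 2, 3 and 5 lesions each and the uneven split, coverage is 91% to 99% and false declaration at 0.10 is at most 1.5%. In the 0.90/0.05 case mean width grows from 0.32 to 0.53 (3 each) and from 0.25 to 0.51 (5 each). The chance of passing stays above 99% with equal counts. If one subject supplies 10 of 30 lesions, it falls from about 99.7% under the current test to 87% (0.90/0.05) or 92% (0.80/0.10). That is a real cost, but in that setting the unadjusted interval covers only 71% or 82%. With 10 clusters no method is perfect, and another cluster-based method would also answer the point if specified in advance.

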# 1 PROTOCOL SUMMARY

## 1.1 Study Synopsis

Title:	Single Dose Investigator Initiated Pilot Study to Investigate CYTALUX (pafolacianine) for Intraoperative Imaging of Patients with Endometrial Cancer Planned for Surgery
Study Description:	
This is a single center, single dose, open-label investigator-initiated pilot study in adult subjects with a primary diagnosis of endometrial cancer who are being evaluated for surgery.
 
Subjects will receive one dose of CYTALUX™ (pafolacianine) injection intravenously prior to the planned diagnostic laparoscopies. This hour-long infusion will be completed from 1 hour to up to 168 hours (7 days) prior to intraoperative near-infrared (NIR) imaging for the planned surgery. All subjects participating in the study are expected to receive CYTALUX™ (pafolacianine) injection and standard care laparoscopic evaluation of disease. Intraoperative imaging with Cytalux will be performed for assessment of disease detection in patients who are being evaluated to undergo surgery for endometrial cancer. Any tissues removed as part of standard of care will undergo assessment with NIR light imaging prior to and after resection. This will be then compared to gold standard histologic confirmation by pathology.

Objectives:	
Primary Objective
 
To assess the ability of CYTALUX™ (pafolacianine) injection used with near-infrared (NIR) fluorescent imaging for the detection of malignant tissue in subjects undergoing surgical resection for endometrial cancer
 
Secondary Objectives
 
 
1. To assess the safety of CYTALUX in subjects undergoing surgery for endometrial cancer
 
2. To assess folate receptor (alpha and beta expression) in resected specimens
 
 
Exploratory Objectives
 
 
1. To assess the feasibility of using genomic markers to predict utility of CYTALUX with NIR imaging
 
2. To assess the feasibility of CYTALUX to identify sentinel lymph nodes
 

Endpoints:	
Primary Endpoint
 
The primary efficacy endpoint is the sensitivity of CYTALUX with NIR imaging for detection of malignant lesions. Sensitivity is defined as the proportion of fluorescent light positive lesions that are histologically

[figure not shown]
03 Sep 2025

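### Section 9.2.2 declares efficacy confirmed once lesion sensitivity is shown to exceed 10%; over an assumed 10 to 50 lesions, an observed 40% down to 20% would pass

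*Protocol*

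**What the plan says.** Section 9.1 defines the primary endpoint as lesion-level sensitivity: fluorescent lesions that prove malignant on histology, "relative to the total number of lesions confirmed to be cancer". Section 9.2.2 analyses it by a "one-sample test for a proportion via an exact binomial test conducted at the two-tailed alpha level of 0.05". The null value is given in one sentence: "The test will compare the observed proportion against a threshold of 0.10". The verdict follows: the efficacy of the drug with fluorescent imaging "will be confirmed if the null hypothesis is rejected and the observed proportion is greater than 0.10". A two-sided 95% confidence interval is to be calculated as well, but it plays no part in the verdict.

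The synopsis (section 1.1) describes a "single center, single dose, open-label investigator-initiated pilot study" and adds: "This study plans to enroll 10 subjects". The protocol gives no expected sensitivity, expected number of lesions or power reasoning. Section 8.1.3 affects the lesion count: when an organ or large piece of tissue with several lesions is removed whole, "one grossly positive lesion will be utilized for the purposes of calculating sensitivity and FR expression".

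**The concern.** A rejected null supports only the statement opposite to that null. Here that statement is that sensitivity is above 10%, which is compatible with an agent that leaves most cancers dark. For 'confirmed' to follow, 0.10 would have to be the lowest sensitivity at which the technique is worth using, and the protocol never says so.

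Two background figures might be taken as support, but neither is a sensitivity and neither is linked to 0.10. Section 2.1 cites receptor expression in over 80% of advanced or recurrent tumours. Section 2.3 cites additional cancer or positive margins in 25% to 40% of subjects in earlier studies.

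Section 2.1 presents the agent as an aid to complete staging and resection, so cancers that do not fluoresce are the failures that matter. If the rule is followed as written, a study in which most confirmed cancers were missed must still be reported as confirming efficacy.

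A secondary point is that sensitivity contains no false-positive term, while section 8.3.3 warns of false positives and of fluorescence in normal and inflamed tissue. Passing this rule alone could therefore not establish efficacy.

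**Working it through.** The protocol states no power or sample-size figure to reproduce, so the check applies its own rule.

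**Inputs from the protocol:** null value 0.10, exact binomial test, two-tailed alpha 0.05, observed proportion above 0.10 (section 9.2.2); lesion-level denominator (section 9.1); 10 subjects (section 1.1).

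**Assumptions:** n = 10 to 50 confirmed malignant lesions, treated as independent, as the stated test does. Low counts are plausible given the one-lesion rule in section 8.1.3. The protocol names neither the two-sided p-value convention nor the interval method, so two conventions are shown, with Clopper-Pearson intervals.

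**Formulas.** With X ~ Binomial(n, 0.10), find the smallest k with k/n > 0.10 and p ≤ 0.05, where p is either
- the minimum-likelihood p: the total probability of all outcomes no more likely than k; or
- the doubled-tail p: 2 × P(X ≥ k), which requires P(X ≥ k) ≤ 0.025.

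The pass probability at true sensitivity s is P(X ≥ k) with X ~ Binomial(n, s).

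**Examples.**
- n = 10: P(X ≥ 3) = 0.0702 fails and P(X ≥ 4) = 0.0128 passes, so k = 4.
- n = 20: P(X ≥ 5) = 0.0432. This passes by minimum likelihood (p = 0.0432) but not when doubled (0.0864). P(X ≥ 6) = 0.0113 passes both.
- n = 50: P(X ≥ 9) = 0.0579 fails and P(X ≥ 10) = 0.0245 passes, so k = 10.

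**Results.** Where the conventions differ, the doubled-tail value is in brackets. The interval is for the stricter count.

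| Lesions | Smallest pass | Observed | Exact 95% CI | Pass probability, s = 0.25 | Pass probability, s = 0.30 |
|---|---|---|---|---|---|
| 10 | 4 | 40% | 0.12–0.74 | 22% | 35% |
| 20 | 5 (6) | 25% (30%) | 0.12–0.54 | 59% (38%) | 76% (58%) |
| 30 | 7 (8) | 23% (27%) | 0.12–0.46 | 65% (49%) | 84% (72%) |
| 40 | 9 | 22.5% | 0.11–0.38 | 70% | 89% |
| 50 | 10 | 20% | 0.10–0.34 | 84% | 96% |

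**Reading.** Boundary results miss from 1 − 0.40 = 60% to 1 − 0.20 = 80% of confirmed cancers. At 30, 40 and 50 lesions, the whole interval of a boundary result lies below 0.50, yet the verdict is confirmed efficacy.

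The fall from 40% to 20% is not strictly monotone, because the test is discrete: the doubled-tail rule needs 5/12 (41.7%), and the minimum-likelihood rule passes 9/47 (19.1%). Below 10 lesions the bar is generally higher (3/5 = 60%, 4/9 = 44%). In every case the number of lesions sets the bar, not a judgement of useful sensitivity.

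**The case against.** A low null value is not in itself an error. In a pilot, rejecting 10% is a coherent test for a minimal signal, and the rationale for 0.10 could stand in a statistical analysis plan that is not shown. This is fair, and the point does not rest on the missing rationale alone. It rests on the protocol's own sentence, which attaches a verdict of confirmed efficacy to that rejection. A minimal-signal test supports saying that a signal was seen.

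The confidence interval is reported too, so a reader of 10/50 would see 0.10 to 0.34, and no go/no-go decision in the protocol depends on the verdict. This limits the harm, but the prespecified conclusion would still contradict the interval printed beside it.

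The lesion count is assumed, and 20% needs 50 lesions, or five per subject. At 10 lesions an agent with true sensitivity 0.30 passes only 35% of the time, and one with true sensitivity 0.80 passes more than 99% of the time. All of this stands: the problem is small at low counts and grows with n. Lesions within a subject are also unlikely to be independent, so the pass probabilities are approximate. The logical gap between exceeding 10% and confirmed efficacy does not depend on n.

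Finally, sensitivity by definition ignores false positives, and the primary objective is detection. A false-positive summary is therefore an optional addition, not the correction of an error.

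**Conclusion.** The concern holds. The test in section 9.2.2 can show that lesion sensitivity exceeds 10%; it cannot confirm efficacy, and the protocol offers nothing to bridge the two. Under the assumption of 10 to 50 independent malignant lesions, the size of the gap is a passing threshold of roughly 40% down to 20% observed sensitivity. The defect is confined to the decision rule: the data, the sensitivity estimate and its interval remain usable. It should be corrected before results are known, because the rule as written prescribes a conclusion stronger than its evidence.

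**What to change.** In section 9.2.2, delete the sentence that declares efficacy confirmed. Make the observed sensitivity with its two-sided 95% confidence interval the primary result, described as pilot estimation.

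If the sponsor wishes to keep a test, replace 0.10 with a minimum useful sensitivity justified in the protocol, and require the lower confidence limit to exceed it. The new threshold does most of the work. Naming the limit also settles the p-value convention: 5/20 passes by minimum likelihood, although its exact interval (0.09 to 0.49) includes 0.10.

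Optionally, report alongside it the proportion of excised fluorescent lesions that are benign on histology. These data are already collected, but they cover excised lesions only, because excision is at the investigator's discretion (section 8.1.3).

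The cost is wording: no new patients, visits or data. The sponsor gives up an easily reached claim. With a higher threshold a small pilot may well not pass: purely for illustration, an exact lower limit above an assumed 0.50 needs 9/10, 15/20, 21/30, 27/40 or 33/50. Estimation is therefore the simpler choice.
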